8.6.2. Outcomes

Venous thromboembolic events

In the primary analysis, venous thromboembolic events will be identified by diagnostic codes for pulmonary embolism or deep vein thrombosis. In a secondary analysis pulmonary embolism and deep vein thrombosis will be assessed separately. We will also assess portal vein thrombosis, splanchnic venous thrombosis (SVT) and cerebral venous sinus thrombosis separately.

Arterial thromboembolic events

In the primary analysis, arterial thromboembolic events will be identified by an acute myocardial infarction or acute ischemic stroke. In a secondary analysis acute myocardial infarction and acute ischemic stroke will be assessed separately. We also identify stroke in general, for which we will include both ischemic, haemorrhagic and non-specifically recorded stroke.

Cardiovascular events

Instances of heart failure, cardiac arrhythmia, and angina will be identified. In addition, major cardiovascular events (MACE) will be identified by heart failure, acute myocardial infarction, or stroke, or the occurrence of sudden cardiac death. As a sensitivity analysis, we will require that events were identified by hospitalisation admission or discharge records.

Table 6. Operational Definitions of Outcome

Outcome name	Details	Primary outcome?	Type of outcome	Washout window	Care Settings ¹	Code Type	Diagnosis Position ²	Applied to study:	Measurement characteristics/validation	Source of algorithm
Venous thromboembolic events	venous thromboembolic events will be identified by diagnostic codes for pulmonary embolism or deep vein thrombosis	Yes	Binary, time-to-event	[-183,-1]	IP,OP	SNOMED	n/a	All included cohorts	n/a	n/a
Arterial thromboembolic events	arterial thromboembolic events will be identified by an acute myocardial infarction or acute ischemic stroke	Yes	Binary, time-to-event	[-183,-1]	IP,OP	SNOMED	n/a	All included cohorts	n/a	n/a
Cardiovascular events	heart failure, cardiac arrhythmia, and angina will be identified.	No	Binary, time-to-event	[-183,-1]	IP,OP	SNOMED	n/a	All included cohorts	n/a	n/a
major cardiovascular events (MACE)	MACE will be identified by heart failure, acute myocardial infarction, or stroke, or the occurrence of sudden cardiac death.	No	Binary, time-to-event	[-1835,-1]	IP,OP	SNOMED	n/a	All included cohorts	n/a	n/a
pulmonary embolism		No	Binary, time-to-event	[-183,-1]	IP,OP	SNOMED	n/a	All included cohorts	n/a	n/a

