Outcome	Myocardial infarction
4119457	Acute Q wave infarction - anterolateral
4119943	Acute Q wave infarction - anteroseptal
4121464	Acute Q wave infarction - inferior
4121465	Acute Q wave infarction - inferolateral
4124684	Acute Q wave infarction - lateral
4119948	Acute Q wave infarction - widespread
4126801	Acute Q wave myocardial infarction
4296653	Acute ST segment elevation myocardial infarction
46270162	Acute ST segment elevation myocardial infarction due to left coronary artery occlusion
761737	Acute ST segment elevation myocardial infarction due to occlusion of circumflex coronary artery
46270163	Acute ST segment elevation myocardial infarction due to right coronary artery occlusion
43020460	Acute ST segment elevation myocardial infarction involving left anterior descending coronary artery
45766076	Acute ST segment elevation myocardial infarction of anterior wall involving right ventricle
761736	Acute ST segment elevation myocardial infarction of anteroapical wall
46270159	Acute ST segment elevation myocardial infarction of anterolateral wall
46270160	Acute ST segment elevation myocardial infarction of anteroseptal wall
45766116	Acute ST segment elevation myocardial infarction of inferior wall
45766151	Acute ST segment elevation myocardial infarction of inferior wall involving right ventricle
35611570	Acute ST segment elevation myocardial infarction of inferolateral wall
35611571	Acute ST segment elevation myocardial infarction of inferoposterior wall
46274044	Acute ST segment elevation myocardial infarction of lateral wall
46270161	Acute ST segment elevation myocardial infarction of posterior wall
46273495	Acute ST segment elevation myocardial infarction of posterobasal wall

	Phase II C3-001 – Study Protocol	
	Author(s): [name], [name]	Version: v3.1
	Dissemination level: public	

46270158	Acute ST segment elevation myocardial infarction of posterolateral wall
46270164	Acute ST segment elevation myocardial infarction of septum
45766075	Acute anterior ST segment elevation myocardial infarction
4178129	Acute anteroapical myocardial infarction
4267568	Acute anteroseptal myocardial infarction
312327	Acute myocardial infarction
44782769	Acute myocardial infarction due to left coronary artery occlusion
44782712	Acute myocardial infarction due to right coronary artery occlusion
45766115	Acute myocardial infarction during procedure
434376	Acute myocardial infarction of anterior wall

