45766150	Acute myocardial infarction of anterior wall involving right ventricle
438438	Acute myocardial infarction of anterolateral wall
4243372	Acute myocardial infarction of apical-lateral wall
4108669	Acute myocardial infarction of atrium
4151046	Acute myocardial infarction of basal-lateral wall
4275436	Acute myocardial infarction of high lateral wall
438170	Acute myocardial infarction of inferior wall
45771322	Acute myocardial infarction of inferior wall involving right ventricle
438447	Acute myocardial infarction of inferolateral wall
441579	Acute myocardial infarction of inferoposterior wall
436706	Acute myocardial infarction of lateral wall
4324413	Acute myocardial infarction of posterobasal wall
4051874	Acute myocardial infarction of posterolateral wall
4303359	Acute myocardial infarction of septum
4147223	Acute myocardial infarction with rupture of ventricle
4145721	Acute non-Q wave infarction
4119944	Acute non-Q wave infarction - anterolateral
4119456	Acute non-Q wave infarction - anteroseptal
4119945	Acute non-Q wave infarction - inferior
4119946	Acute non-Q wave infarction - inferolateral
4121466	Acute non-Q wave infarction - lateral
4124685	Acute non-Q wave infarction - widespread
4270024	Acute non-ST segment elevation myocardial infarction
35610091	Acute nontransmural myocardial infarction
319039	Acute posterior myocardial infarction
444406	Acute subendocardial infarction
35610093	Acute transmural myocardial infarction
4119947	Acute widespread myocardial infarction
37109912	Arrhythmia due to and following acute myocardial infarction
438172	Atrial septal defect due to and following acute myocardial infarction
4124687	Cardiac rupture due to and following acute myocardial infarction

	Phase II C3-001 – Study Protocol	
	Author(s): [name], [name]	Version: v3.1
	Dissemination level: public	

4215259	First myocardial infarction
4108678	Hemopericardium due to and following acute myocardial infarction
4173632	Microinfarct of heart
45771327	Mitral valve regurgitation due to acute myocardial infarction with papillary muscle and chordal rupture
45766214	Mitral valve regurgitation due to acute myocardial infarction without papillary muscle and chordal rupture
45766212	Mitral valve regurgitation due to and following acute myocardial infarction
4323202	Mixed myocardial ischemia and infarction
4329847	Myocardial infarction
37309626	Myocardial infarction due to demand ischemia
4170094	Myocardial infarction in recovery phase

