4200113	Non-Q wave myocardial infarction
4030582	Postoperative myocardial infarction
35610087	Postoperative nontransmural myocardial infarction
4206867	Postoperative subendocardial myocardial infarction
35610089	Postoperative transmural myocardial infarction
4207921	Postoperative transmural myocardial infarction of anterior wall
4209541	Postoperative transmural myocardial infarction of inferior wall
37109911	Pulmonary embolism due to and following acute myocardial infarction
4108679	Rupture of cardiac wall without hemopericardium as current complication following acute myocardial infarction
4108219	Rupture of chordae tendinae due to and following acute myocardial infarction
4124686	Silent myocardial infarction
765132	Subendocardial myocardial infarction
45766114	Subsequent ST segment elevation myocardial infarction
45766113	Subsequent ST segment elevation myocardial infarction of anterior wall
45773170	Subsequent ST segment elevation myocardial infarction of inferior wall
4108217	Subsequent myocardial infarction
4108677	Subsequent myocardial infarction of anterior wall
4108218	Subsequent myocardial infarction of inferior wall
45766241	Subsequent non-ST segment elevation myocardial infarction
4108680	Thrombosis of atrium, auricular appendage, and ventricle due to and following acute myocardial infarction
439693	True posterior myocardial infarction
37109910	Ventricular aneurysm due to and following acute myocardial infarction
Outcome	Intestinal infarction
4195665	Gastrointestinal tract vascular insufficiency
4148299	Ischemic colitis
4173167	Mesenteric embolus
4317289	Thrombosis of mesenteric vein
4319280	Acute bowel infarction
4144032	Mesenteric thrombus and/or embolus

	Phase II C3-001 – Study Protocol	
	Author(s): [name], [name]	Version: v3.1
	Dissemination level: public	

45757410	Acute thrombosis of mesenteric vein
45757409	Chronic thrombosis of mesenteric vein
44811741	Acute ischaemia of large intestine
44811740	Acute ischaemia of small intestine
37117790	Insufficiency of mesenteric artery
37016198	Epiplaic appendagitis
35622081	Nongangrenous ischemic colitis
35622080	Gangrenous ischemic colitis
4345926	Abdominal angina
4342767	Transient ischemic colitis
4341648	Hemorrhagic infarction of intestine
4341646	Occlusive mesenteric ischemia
4340939	Non-occlusive mesenteric ischemia
4340378	Transmural infarction of intestine
4340375	Focal segmental ischemia of small intestine
4318537	Large bowel gangrene

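### The preliminary code lists for the primary arterial outcome contain concepts that do not identify a new acute event, and one pulmonary embolism concept counts as both a venous and an arterial event.

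*Protocol*

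**What the plan says.** Section 8.6.2 states the primary arterial outcome as follows: "arterial thromboembolic events will be identified by an acute myocardial infarction or acute ischemic stroke". For the venous outcome, "venous thromboembolic events will be identified by diagnostic codes for pulmonary embolism or deep vein thrombosis". Section 7 and Table 6 carry the same definitions.

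The concepts behind these definitions are in Appendix I, Table 2, which is labelled preliminary. The only MI list is headed "Myocardial infarction", without the word acute. Among its entries are:

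- "Myocardial infarction in recovery phase" (4170094);
- "Silent myocardial infarction" (4124686);
- "Ventricular aneurysm due to and following acute myocardial infarction" (37109910);
- "Mitral valve regurgitation due to and following acute myocardial infarction" (45766212);
- "Pulmonary embolism due to and following acute myocardial infarction" (37109911), which also stands in the PE list.

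The ischaemic stroke list includes silent cerebral infarct (36717605).

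Table 4 excludes people with the outcome in the 183 days before index, in all five cohorts. Table 9 adds sensitivity analyses with a 91-day washout and with exclusion of any VTE or ATE history. A note after Appendix I, Table 4 says that CohortDiagnostics will be run on code counts and patient characteristics before the concept sets are finalised.

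**The concern.** The analysis runs on the code list, not on the sentence in section 8.6.2. A recovery-phase code says by its name that the infarct has already happened. A silent infarct may be found at some unknown time after it occurred. A ventricular aneurysm or mitral regurgitation following an infarct may be recorded after the infarct itself. If such a record falls after index, it can be counted as a new arterial event on a date that is not the date of an acute event.

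The shared PE concept raises a second problem. One record, dated at the embolism, enters both primary outcomes. In objective 4b (section 8.8.4), VTE and ATE are time-dependent exposures for transitions to hospital admission and death, and that one record would switch on both at the same moment.

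The ATE incidence rates, the risk-factor models, the multistate models and the SIRs all use this outcome. Section 11 states that outcomes will not be validated by case note review, so no later step would correct a wrong code.

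**Working it through.** No figure in the protocol depends on this point, so there is none to reproduce. The check is a count of the listed concepts, an intersection of two lists, and a trace through the washout.

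**1. Composition of the MI list (Appendix I, Table 2).** There are 96 distinct concepts:

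| Wording of the name | Concepts |
|---|---|
| Begins with acute | 61 |
| Names a complication due to or following acute MI | 12 |
| Does not contain the word acute | 23 |
| Total | 61 + 12 + 23 = 96 |

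**2. Which of these clearly fail to identify a new acute event.** The 23 names without acute are not all non-acute. First, subsequent and postoperative MI may be acute events, and the unspecified MI concept (4329847) is ambiguous. The clear cases are recovery phase and silent, which makes 2.

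Of the 12 complications, 1 is the PE concept. Four name conditions that may be recorded after the infarct: ventricular aneurysm (37109910), arrhythmia (37109912), atrial septal defect (438172) and mitral regurgitation (45766212). The remaining 12 − 1 − 4 = 7, such as cardiac rupture and hemopericardium, may mark a current infarct.

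MI concepts in question: 2 + 4 + 1 = 7 of 96. Silent cerebral infarct in the stroke list makes 8 concepts in all. A share of concepts is not a share of records.

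**3. Overlap of the PE and MI lists.** The PE list has 21 concepts. Its intersection with the 96 MI concepts is exactly one, 37109911.

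**4. Trace through the washout.** Take an infarct recorded 184 or more days before index.

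- Primary analysis: the record lies outside the 183-day window, so the person enters the cohort. Section 8.6.3 confirms that MI history before the washout is kept as a covariate.
- If a recovery-phase or complication code is then the first listed code after index, it is counted as an incident ATE.
- Any-history sensitivity analysis: the person is excluded, provided that the earlier infarct was recorded. If it was not, as is possible with a silent infarct, the person stays in.

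**5. Effect on the SIR.** Let *o* be the true observed events and *e* the events expected from true background events. Let *a* and *b* be the additions to each from non-incident records. The reported ratio is (*o* + *a*)/(*e* + *b*), which exceeds *o*/*e* only if *a*/*b* > *o*/*e*. The protocol gives neither *a* nor *b*, and because the same lists apply to the background cohort, *b* cannot be taken as zero. If *a* = *b* > 0 and the true ratio is above 1, the reported ratio moves towards 1. If *a*/*b* is larger than the true ratio, it moves up.

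**The case against.** The strongest reply is that the lists are openly preliminary and have a stated revision step. That is correct and lowers the weight of the point. The step as described covers code counts and patient characteristics, however. It promises no check of acuteness or of overlap between outcomes, so it cannot be relied on to find these concepts.

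A second reply is that the any-history washout removes sequelae of an earlier infarct. It does so only where that infarct was recorded, and only in a sensitivity analysis.

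A third is that the complication names give no interval; one even refers to a current complication. This stands. A reader might infer that all 12 complication concepts are late sequelae and that all 14 concepts (12 plus recovery phase and silent) are wrong. The names do not support that, which is why only four complication concepts and the PE concept are questioned.

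A fourth is that 37109911 names both an embolism and an acute MI in one person, and that VTE and ATE are analysed separately with no pooled count planned. It is true that nothing is counted twice within one outcome. What remains is that the arterial event takes the date of the embolism, and that one record switches on both exposures in objective 4b.

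**Conclusion.** The point holds as a mismatch between the written definition of a primary outcome and its preliminary code list. It concerns seven of the 96 MI concepts and one stroke concept. It rests on the names of the listed concepts and on the assumption that the lists would be used as printed.

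A reader might go further and infer that the 30-day ATE rate and the SIR after COVID-19 are inflated, because people with COVID-19 have more contacts and imaging and so more old infarcts are found. The protocol does not support this. It gives no code frequencies and no information on contact or imaging rates, and it applies the same codes and the same washout to the background cohort, which is followed through 2017 to 2019. Neither the size nor the direction of the effect on the SIR can be stated, and no percentage should be attached to it.

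The correction should be made because it is cheap now and because the result would otherwise not measure what section 8.6.2 says it measures.

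**What to change.** Before the concept sets are finalised:

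- Exclude from the primary ATE definition 4170094, 4124686, 36717605, 37109910, 37109912, 438172 and 45766212.
- Keep 37109911 under PE only, and exclude it from the MI set.
- Make these explicit exclusions and do not merely delete the rows. The note after Appendix I, Table 4 says that concept IDs include descendants. It is unclear whether this governs Table 2, but if it does, a broad parent such as 4329847 may bring deleted concepts back.
- Keep complication concepts that may mark a current infarct, for example cardiac rupture and hemopericardium.
- Report the broad list as a sensitivity analysis.

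The cost is a code-list edit and one further sensitivity run. The downside is a small loss of sensitivity where an excluded concept was the only record of a true acute event; the broad-list analysis will show how much the result depends on it.

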APPENDIX I, TABLE 3: PRELIMINARY CONCEPTS FOR OTHER OUTCOMES

Concept id	Concept name	group	domain
------------	--------------	-------	--------

	Phase II C3-001 – Study Protocol	
	Author(s): [name], [name]	Version: v3.1
	Dissemination level: public	

4306655	Death	Death	Outcome	Observation
9201	Inpatient Visit	IP/ER	Outcome	Visit
262	Emergency Room and Inpatient Visit	IP/ER	Outcome	Visit
9203	Emergency Room Visit	IP/ER	Outcome	Visit

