8.5 Study Population with inclusion and exclusion criteria

Five non-mutually exclusive study cohorts for the analyses will be defined:

- 1. General population cohort for pre-pandemic background rates** will have
 - Individuals will start contributing as of 1st January 2017, or when they have at least 365 days of data availability.
 - follow-up for this cohort will run up to 31 December 2019.
- 2. Persons tested positive for SARS-CoV-2 or with a clinical diagnosis of COVID-19 during the Omicron period** will
 - have either a positive test result for SARS-CoV-2 or a clinical diagnosis of COVID-19 on or after 1st December 2021 (with the index date being whichever date comes first if both occur)
 - have no positive test result for SARS-CoV-2 or clinical diagnosis of COVID-19 within 3 months prior to the index date.
 - have at least 365 days of data availability prior to index date
- 3. Persons hospitalised with COVID-19 during the Omicron period** will have
 - a hospitalisation on or after 1st December 2021 (with the index date the date of hospital admission),
 - a record of a clinical diagnosis of COVID-19 or a positive test result for SARS-CoV-2 in the period between 3 weeks prior to and up to 3 days following the index date.
 - have no diagnosis of COVID-19 or a positive test result for SARS-CoV-2 between 3 months and 3 weeks prior to index date.
 - have no COVID-19 hospitalisation within 3 weeks prior to the index date.
 - have at least 365 days of data availability prior to index date
- 4. Persons requiring intensive services during a hospitalisation with COVID-19 during the Omicron period** will have
 - intensive services initiated during a hospitalisation as described in cohort 3 (with the index date the date at which intensive services were initiated)
 - patients will have had a confirmatory diagnosis or test result of COVID-19 (both as defined above) within a time window from 3 weeks to their index date up to three days following their index date.
 - have at least 365 days of data availability prior to index date
- 5. Persons vaccinated against SARS-CoV2 infection**
 - a vaccination record identified by brand (with the index date the date of vaccination record)

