8.8.2 Incidence of study outcomes

The incidence of each study outcome described in section 8.6.2 will be estimated during 30-, 60-, and 90- and 180-days following the index date for each cohort of interest with 95% confidence intervals in each database. The 90-day cumulative incidence of study outcomes will be estimated. Given the risk of mortality among patients with COVID-19, particularly among those hospitalised, the competing risk of mortality will be accounted for by estimating cumulative incidence functions. If death is not available, cumulative incidence will be estimated using the Kaplan-Meier approach. As well as estimating the incidence of outcomes for each study cohort as a whole, incidence will also be estimated by age group stratified by sex. Other stratifications by prior COVID-19 diagnosis, prior SARS-CoV-2 vaccination, whether patients were hospitalised on the index date or where immunocompromised on the index date will also be performed.

8.8.3 Assessing the association between risk factors for thromboembolic events and COVID-19 during the Omicron period

To assess the association between potential risk factors on the incidence of venous and arterial thromboembolic events among patients with COVID-19 during the Omicron period, cause-specific Cox models will be used to calculate hazard ratios for the incidence of venous and arterial thromboembolic events for each of the COVID-19 cohorts. Adjusted models will evaluate potential predictors including age, sex, prior COVID-19 infection status, prior vaccination status, cancer, whether patients were immunocompromised on the index date, prior use of antithrombotics, prior use of corticosteroids, and pre-index comorbidities listed in section 8.6.3.

8.8.4 Risks of COVID-19 “worsening” (hospital admission or death) stratified by thromboembolic event occurrence during the Omicron period

[This analysis will only be conducted in the SIDIAP data given the availability of hospital data]

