A multistate-type modelling approach will be used to assess risks of COVID-19 worsening during the period when Omicron was the dominant variant, stratified by thromboembolic event occurrence. Multistate models allow for a consideration of individuals progression to multiple events of interest, extending on competing risk models by also describing transitions to intermediate events. [24] In the context of COVID-19, use of intensive care services during a hospitalisation can be considered as key intermediate events between testing positive for SARS-COV-2 or having a clinical diagnosis of COVID-19 in an outpatient setting on the one end to a COVID-19-related death on the other.

[figure not shown]
	Phase II C3-001 – Study Protocol	
	Author(s): [name], [name]	Version: v3.1
	Dissemination level: public	

Venous thromboembolism and arterial thromboembolism will be assessed separately, as time -dependent exposures for the following transitions:

- (1) from outpatient COVID-19 diagnosis or PCR test positive to hospitalised with COVID-19
- (2) from outpatient COVID-19 diagnosis or PCR test positive to death (without a COVID-19 hospitalisation in between)
- (3) from being hospitalised with COVID-19 to death

Figure 1 shows an exemplar model for assessing COVID-19 worsening stratified by venous thromboembolic event, where individuals would begin by being identified as having a positive test for SARS-CoV-2 or clinical diagnosis of COVID-19 in an outpatient setting and then would progress through the various hospitalisation-related states, and would capture deaths (either after such a hospitalisation or directly after the test, for those individuals who were not hospitalised before their deaths).

Figure 1. Example multi-state model framework to assess COVID-19 worsening stratified by venous thromboembolic event

Cause-specific Cox models within the multistate framework will be used to estimate hazard ratios associated with the risk factors of interest. This approach will allow for the factors of interest to have a different effect by the transition of interest and, where the model includes a state representing deaths, will account for the competing risk of mortality. Models will be adjusted for age and sex.

8.8.5 Contextualising incidence rates for thromboembolic events in COVID-19 during the period when Omicron was the dominant variant

	Phase II C3-001 – Study Protocol	
	Author(s): [name], [name]	Version: v3.1

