	Author(s): [name], [name]	Version: v3.1
	Dissemination level: public	

Condition	Inclusion, incl. descendants	Exclusion, incl. descendants
Diabetes mellitus	201820, 442793, 604741, 760977, 760978, 760979, 760980, 760989, 761050, 761063, 765375, 4019513, 4034961, 4055679, 4060085, 4065354, 4129379, 4130165, 4144221, 4146514, 4175440, 4182243, 4219466, 4220981, 4242853, 4305491, 4307799, 37018224, 40482801, 40484648, 40484649, 40485020, 42536400, 42689695, 43020791, 45766963, 45768456	
Osteoporosis	80502, 36716194, 4109181, 44783850, 37204244	
Smoking (current or past)	619068, 437264	
Alcohol abuse	436607, 4322643, 4030588, 195300, 4106575, 378421, 4214950, 4302744, 4176651, 4202330, 46269816, 46269817, 37016176, 45757494, 318773, 36714559, 619608, 45757783, 35610532, 46269818, 3655834, 44782445	
Drug abuse	606210, 436954, 4127868, 4022666, 40480941, 40482269, 4295481	
Drug abuse	42529475, 4168205, 4239438, 4206984, 4219142, 3022196, 36031658, 36031249, 4017177, 4229859, 42529480, 4036792, 4038240, 4037138, 42539778, 1616455	
Alcohol abuse	4116983, 4053784, 45766930, 4080065, 36674487, 45772695, 44793164, 37206970, 4207141, 44792459, 3036878, 762596, 4145860, 4042872, 4027638, 44786671, 432456, 44786700, 40481082, 4038704, 3027199, 608490, 44812667	
Smoking (current or past)	44788975, 44788976, 762499, 3012697, 4052948, 600776, 44786669, 762498, 4131520, 37395605, 1616974, 42528924, 44804450, 4206526, 4203874, 4046886, 4141787, 44809281	

Concept IDs include descendants unless highlighted as being excluded. By OMOP standards descendants automatically include the ancestor.

Before finalizing the concept sets, CohortDiagnostics will run on cohorts created using the initial concept sets to check code counts and patient characteristics which might give indications to adjust the concept sets.

	Phase II C3-001 – Study Protocol	
	Author(s): [name], [name]	Version: v3.1
		Dissemination level: public

	Phase II C3-001 – Study Protocol		
	Author(s): [name], [name]	Version: v3.1	
	Dissemination level: public		

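### The preliminary outcome codes put stand-alone emergency room visits in one group with inpatient admissions, which contradicts the protocol's admission-based definitions of hospitalisation and worsening

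*Protocol*

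**What the plan says.** **Code list.** Appendix I, Table 3 is headed "PRELIMINARY CONCEPTS FOR OTHER OUTCOMES". It has four entries in two groups. One group is Death. The other, IP/ER, holds "Inpatient Visit" (9201), "Emergency Room and Inpatient Visit" (262) and "Emergency Room Visit" (9203), all labelled as outcomes in the visit domain. No other visit code appears in the appendix.

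**Analysis text.** The title of section 8.8.4 defines COVID-19 worsening in brackets and continues: "hospital admission or death) stratified by thromboembolic event occurrence during the Omicron period". Its first transition runs "from outpatient COVID-19 diagnosis or PCR test positive to hospitalised with COVID-19", and its third starts from the hospitalised state and ends in death.

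**Cohort text.** Section 8.5 requires, for cohort 3, "a hospitalisation on or after 1st December 2021 (with the index date the date of hospital admission"). Section 8.6.1 sets the diagnosis or test window from 21 days before admission to three days after it. Tables 2 and 5 give the care setting as IP. The Table 2 key lists ED separately from IP, and its cohort 3 row sends the reader to the appendix for codes.

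**Status of the list.** A note under Appendix I, Table 4 says: "Before finalizing the concept sets, CohortDiagnostics will run on cohorts created using the initial concept sets". The sets may be adjusted afterwards.

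**The concern.** The body text and the code list describe different events. By its name, 262 already covers people who came through the emergency room and were admitted, so 9203 adds emergency contacts with no recorded admission. A programmer who builds hospitalisation from the appendix would find the IP/ER group and no narrower one.

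Hospitalisation is the index event of cohort 3, a stratifier for cohorts 2 and 5 (location at index date, section 8.6.3), the end of transition (1) and the start of transition (3). Objective 4b is listed under the primary research question in section 7 and can be run in SIDIAP only, so no second database could expose a wrong definition.

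**Working it through.** The protocol states no figure on this point, so the check sets the texts side by side and follows the consequences.

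**1. Do the definitions agree?**

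| Place | Event required | Emergency visit without admission counts? |
|---|---|---|
| 8.8.4, title | Hospital admission or death | No |
| 8.5, cohort 3 | Hospitalisation, indexed on admission date | No; there is no admission date |
| 8.6.1 | Hospitalisation, window set around admission | No |
| Table 2, cohort 3 | Setting IP; key keeps ED apart | No |
| Table 7, location at index date | IP, intensive care | No |
| Appendix I, Table 3 | 9201, 262 or 9203 | Yes, in the IP/ER group |

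Five places require inpatient admission, and the code list is wider than all of them.

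**2. Is Table 3 plausibly the source for hospitalisation?** Its two groups, Death and IP/ER, match the two components of worsening in 8.8.4. Emergency attendance is not among the outcomes in section 8.6.2 or Table 6, so 9203 has no other stated use. The link is an inference, since no sentence makes it.

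**3. What follows if the group is used as written?**
- *Cohort 3.* Its rates would describe a mixture of admitted and never-admitted people. Someone sent home from the emergency room and admitted within three weeks would be indexed on the emergency visit, and the later admission would fail the 8.5 requirement of no COVID-19 hospitalisation in the preceding three weeks.
- *Transition (1).* Emergency-only contacts would count as progression to hospitalisation.
- *Transition (3).* Those same people would become at risk of death from the hospitalised state.

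**4. In which direction would the transition (1) hazard ratio move?** Let HR_adm be the hazard ratio of a thromboembolic event for true admission, HR_ER the hazard ratio for an emergency-only contact, and r the baseline hazard of an emergency-only contact relative to an admission. Combining the two end points gives

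observed HR = (HR_adm + r × HR_ER) / (1 + r).

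This is a weighted average with weights 1/(1 + r) and r/(1 + r). It lies below HR_adm when HR_ER < HR_adm, for example when emergency contacts have nothing to do with the clot. It lies above HR_adm when HR_ER > HR_adm. At r = 0 it equals HR_adm. The protocol gives no value for r, HR_adm or HR_ER, so neither sign nor size can be fixed.

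Timing matters as well. Section 8.8.4 treats venous and arterial events as time-dependent exposures. If a clot is diagnosed at the attendance that ends transition (1), exposure begins on or after the transition date. Unless a tie rule says otherwise, that transition falls in unexposed time.

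**5. How far does it reach?** The setting row of the section 7 table says that inpatient information exists only in SIDIAP, and 8.8.4 is restricted to SIDIAP. Cohort 4 is barely touched, because it also requires ICU admission, ventilation, tracheostomy or ECMO.

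**The case against.** The strongest reply is that Table 3 does not define cohort 3. It is headed as a list of other outcomes, while hospitalisation with COVID-19 is an exposure in section 8.6.1. Table 2 refers cohort 3 to SNOMED codes, and Table 3 holds visit-domain concepts. The appendix is also visibly incomplete: it has no codes for intensive care, ventilation, tracheostomy or ECMO, although Table 2 refers cohort 4 to it. The absence of another inpatient code therefore does not prove that IP/ER is the intended one. The list is preliminary and will be reviewed.

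Much of this stands. A reader might infer that the plan counts people who were never admitted as hospitalised, or as having worsened. The documents do not support that as a settled fact: no passage says it, and the body text says the opposite. A reader might also infer that emergency assessment of a suspected clot must inflate the transition (1) hazard ratio. That is not supported either, for the reasons in step 4 of the working.

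The reply does not remove the contradiction. The purpose of IP/ER is not stated, and 9203 is nowhere excluded from hospitalisation. The planned diagnostics look at code counts and patient characteristics. A valid visit code can look normal on both and still conflict with 8.8.4.

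**Conclusion.** The point holds as an internal contradiction with a conditional consequence. The only written visit code set is broader than the admission-based definitions in sections 8.5, 8.6.1 and 8.8.4 and in Table 2. If it is applied unchanged to hospitalisation, emergency-only contacts would affect cohort 3, the stratification by hospitalisation on the index date, and transitions (1) and (3) of objective 4b, in SIDIAP alone.

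The size cannot be given. SIDIAP is described as primary care data linked to hospital data, with inpatient admissions. Nothing says whether it records emergency visits without admission, and if it does not, the effect is nil. The direction of any bias in transition (1) is likewise open. The conclusion rests on reading IP/ER as the source for hospitalisation, which is reasonable but not stated. It should be corrected before the concept sets are made final.

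**What to change.** In Appendix I, Table 3, define hospitalisation as 9201 or 262 only and remove 9203 from that set. State that this definition applies to cohort 3, to hospitalisation on the index date, and to the objective 4b transitions. If emergency attendance is of interest, list 9203 on its own as a separate descriptive outcome and say what it is for.

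The cost is one concept ID and a sentence of text, with no new data. Fewer events may be labelled as hospitalisation, which loses some precision, but those that remain match the definition in 8.8.4.
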